General Background: Binge drinking is a major public health problem in the United States. The Center for Disease Control (CDC) places alcohol as the number three cause of preventable deaths following nicotine use and overweight (Mokdad et al, 2004). Binge drinking, generally defined as the consumption of five or more standard drinks for a man or four or more drinks for a woman in about a two hour period (see Courtney and Polich 2009), is a major component of excessive alcohol use and a serious problem for the United States. The CDC (2012) report indicated that 17.1% of the adult U.S. population reported one binge drinking episode in the past 30 days in 2010--men (23.2%) vs. women (11.4%) with peak ages 18-24 years (28.2%), 25-34 years (27.9%), and 35-44 years (19.2%). Men reported an average of 5 binge drinking episodes/month with a mean of 9.0 drinks/episode and women 3.2 binge drinking episodes/month at 5.9 drinks/episode. Binge drinking leads to multiple problems, e.g. accidental injury (Gmel et al, 2006), aggressive and violent behavior (Shepard et al, 2006), and high blood pressure (Fan et al, 2008). Additionally, there is increased risk for developing alcohol dependence in individuals that binge drink frequently (Hingson et al, 2006). Overall, binge drinking contributes to more than half of all deaths attributed to alcohol and to three quarters of the economic cost of excessive alcohol use—*binge drinking is a serious public health problem and one that may exceed traditionally defined alcohol dependence in its overall cost to society.*

Binge drinking is a complex construct as it is both a stand-alone phenomenon and also a component of alcohol use disorders. We are focusing on the behavior to allow greater fidelity to the preclinical data where the key behavior was consumption of an intoxicating amount of alcohol in a two hour period, a non-dependent

model (Navarro et al, 2015). The majority of binge drinkers do not have physical dependence (see Woerle et al, 2007), and we are particularly interested in this "developmental" phase towards overt physical dependence as the preclinical literature suggests this phase may be a key time for clinical intervention (Thiele 2012).

Treatment of Binge Drinking with or without Co-Occurring Alcohol Use Disorders

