For this proof of concept trial, it is important to use doses of bupropion that are known to be effective and safe for humans. For bupropion we have selected a 300 mg/d dose of the extended release formulation. The 300 mg dose of bupropion is approved by the FDA for depression and for nicotine dependence. The extended release 300 mg formulation has a lower estimated risk of seizures (0.1%) compared to the 0.4% rate for the immediate release formulation. The 0.1% risk of seizures is comparable to the risk reported with other antidepressants such as sertraline and fluoxetine (FDA labels) and with acamprosate (FDA label), which is approved for alcohol dependence. Furthermore, we will be studying a binge drinking population without evidence of physical dependence, a history of seizures, or a reported history of cocaine use so seizure risk is minimized which has been raised as a concern based on animal studies (Silverstone et al, 2008).

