**Trial Design**: The design is a 1:1 random assignment to placebo or bupropion XL (300mg/d). [name], the study biostatistician, will prepare the randomization schedule and include blocking by gender. Randomization will be based on a stratified block design, with gender and nicotine dependence as the IRB #16-1064 Master Protocol v.3

stratification variable given some evidence of a moderating effect of nicotine dependence on response to alcohol pharmacotherapy (Fucito et al, 2012).

Bupropion XL will be initiated at 150 mg/d on Days 1-4 and increased to 300 mg/d for Days 5-84. Medication is reduced to 150mg/day for 3 days before being stopped at Week 12 UNC Hospital's Investigational Drug Services (IDS) will prepare opaque capsules containing bupropion XL 150/300 mg and matching placebo. Capsules will be inserted into blister packs with each pack containing 1 week of medication. The IDS will receive the randomization schedule from our statistician [name] and prepare the blister packs according to the blocked schedule with blocking for gender

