Initial Treatment Visit (within 21 days screening): Eligible individuals will *not be required to abstain from drinking alcohol* prior to randomization. The study coordinator will administer a breathalyzer test (BAC must be ≤0.04 gms/d) and complete assessments as outlined in Table 1, Protection of Human Subjects. A salivary sample for cotinine to be assayed at UNC will be taken. A 1-week blister pack of bupropion-XL or placebo with written instructions will be dispensed from the Investigational Drug Services according to the randomization block. A 1-week back-up blister pack will dispensed once the participant reaches the maintenance dose in case of delayed appointments or lost doses. Bupropion-XL will be titrated with 150 mg given daily for 4 days followed by 300 mg/d. Participants will be given a calendar style diary to track pill taking, drinking quantity/timing, intoxication and any side effects. Finally, participants will receive Medical Management from a trained clinician.

Subsequent Treatment Visits: See Table 1 in Protection of Human Subjects for a summary of procedures and assessments. Salivary cotinine samples will be obtained at weeks 4, 8 and 12. TLFB and PACS are gathered each visit. Medical monitoring will be conducted by study physicians and will consist of review of vital signs, concomitant medication use, and general inquiries into side effects. Blood pressure readings of >100mm Diastolic or >160mm Systolic will be automatically rechecked. If a participant has sustained, recurrent blood pressure readings above this limit, their medication will be tapered and stopped. The physician may recommend that medication be held or reduced for a period of time to deal with an adverse event, e.g. nausea. The Visit Window is defined as +/-3 days for weekly visits and +/-7 days for visits that occur every 2 weeks.

IRB #16-1064 Master Protocol v.3

Missed Visits are expected. Participants can remain in the study as long as they do not miss more than 2 consecutive visits. If a missed visit has a safety lab test, every effort will be made to schedule the subject as soon as possible to obtain the sample. One month and three months following the last visit subjects will be contacted to update drinking (TLFB), adverse effects and medications.

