Statistical Analysis: Study participants will first be characterized on baseline measures with appropriate methods. We will derive weekly summary scores from the TLFB quantifying the %Binge Drinking Days and the average drinks per binge drinking day per week. Descriptives and exploratory graphing will be used to assess the presence of skew and/or outliers with appropriate transformation implemented as needed. As stated above, our sample sizes are set to assess feasibility and implementation; therefore, the respective analyses, are exploratory, and therefore, not powered, but analyzed in accordance with the methods and recommendations per Kianifard & Islam (2011) for this proof-of-concept study. Per recommendation 4 of Kianfiard & Islam (2011) who describe caution when interpreting analyses from small trials, we will implement

IRB #16-1064 Master Protocol v.3

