
Response, i.e. no binge drinking days in final 6 weeks of medication, tolerability measured via retention time, and number of adverse events reported will be examined with Logistic regression, Cox-Regression, and Ordinal-regression models, respectively with the same contrast comparisons as above focused on the derivation of confidence intervals for the respective contrasts. Moderation of nicotine use will follow the procedure as discussed earlier, where the respective models will be augmented to include the interaction of nicotine use with assignment, with the derivation of the confidence interval for the differences as described above.

DATA MANGEMENT PLAN

The Database will be configured in Microsoft Access or Excel. Discrepancies will be examined and additional data checks completed as indicated. A closed and password-protected data entry system will be used and only

certified study personnel will be able to enter or edit data. Data and user stamping are used to create an audit trail. Range checks, review screens, and error trapping routines are built into the system as quality control procedures. Hardcopy data summaries will be available to the investigators for data analyses. As a final check on data integrity, the investigators and study coordinator will check these outputs against the raw data and resolve any discrepancies. We will be asking subjects to fill out self-ratings on a tablet mobile device. The ratings will be in the form of Qualtrics surveys. No identifying data will be entered into the tablet, just a subject ID number.

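### The only between-arm adverse-event contrast in the text is each participant's total event count, which dilutes an excess of one side effect and could offset it

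*Combined protocol and SAP*

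**What the plan says.** The Statistical Analysis section (under Statistical Plan and Data Analysis) lists response, retention time and adverse events, and assigns a model to each in order: "number of adverse events reported will be examined with Logistic regression, Cox-Regression, and Ordinal-regression models, respectively". Adverse events are therefore analysed as a number per participant by ordinal regression. The results are "focused on the derivation of confidence intervals for the respective contrasts", with a nicotine interaction added. The companion outcome is "tolerability measured via retention time", by Cox regression. The supplied text contains no between-arm analysis by event type, severity, seriousness, relatedness or action taken.

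Three other places bear on what the count would contain.

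- The dose rationale under Research Approach attributes a seizure risk of 0.1% to the extended-release product.
- Subsequent Treatment Visits gives nausea as an example: "The physician may recommend that medication be held or reduced for a period of time to deal with an adverse event, e.g. nausea". It also sets a blood-pressure limit above which medication is tapered and stopped. Side effects are elicited by general inquiry.
- General Background states: "Binge drinking leads to multiple problems, e.g. accidental injury". It goes on to list aggression and high blood pressure.

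Outcome Variables separately says that consequences of binge drinking will be examined. It does not say whether those consequences are kept out of the adverse-event count.

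**The concern.** The title promises safety results and Research Approach promises tolerability results. A single total treats a mild complaint, an event that ends treatment and a seizure as one unit each. This causes two distinct problems.

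- **Dilution.** Events unrelated to the drug add variation to the count, so an excess confined to one side effect is hard to see. This needs no assumption about alcohol.
- **Offset.** If events caused by drinking are recorded as adverse events and the drug reduces drinking, one part of the total falls while another rises. The contrast then estimates the net of the two.

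Either way, an odds ratio near 1 would not show that no particular side effect was more common on bupropion. Both hold even if every participant completes 12 weeks.

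**Working it through.** **Inputs from the documents.** Allocation is 1:1 (Trial Design) and the full sample is 50 (Statistical Analysis), so 25 per arm. Seizure risk is 0.1%. No rate is given for any other adverse event.

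**The plan's own figure.** No sample-size figure is given for adverse events. The one that exists, 30 per arm with a 2:1 nicotine split, gives 30 × 1/3 = 10 in the smaller cell, inside the stated 7 to 10. At 25 per arm it is 25/3 = 8.3, also inside. That 2 × 30 = 60 disagrees with N = 50 is a separate matter; in the check below with graded rates, the pattern is the same at 30 per arm.

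**Assumptions.** Each count is Poisson background events, plus Poisson alcohol-caused events, plus one side effect occurring at most once (10% placebo, 40% bupropion). Background is 1.5 or 0.5 events per person; alcohol-caused events are 0, 0.5 or 1.0 per placebo participant.

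**Method.** Totals were compared by the tie-corrected Wilcoxon test, which is the score test of a proportional-odds model with treatment only. Harm is flagged when two-sided p<0.05 in the harmful direction. The single event type is flagged when the Newcombe 95% interval for the difference in proportions lies above zero.

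**When the offset is complete.** Mean totals are equal when (alcohol-caused rate) × (proportional cut) = (excess of the side effect). Here the excess is 0.40 − 0.10 = 0.30. With 1.0 alcohol-caused event per person, a 30% cut is enough: placebo 1.5 + 1.0 + 0.1 = 2.6; bupropion 1.5 + 0.7 + 0.4 = 2.6.

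**Results, 25 per arm, one side effect 10% v 40%**

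| Background | Alcohol-caused (placebo) | Cut on bupropion | Mean total, placebo / bupropion | Total flags harm | Event type flags harm |
|---|---|---|---|---|---|
| 1.5 | 0 | – | 1.6 / 1.9 | about 13% | about 73% |
| 0.5 | 0 | – | 0.6 / 0.9 | about 26% | about 73% |
| 1.5 | 1.0 | 0% | 2.6 / 2.9 | about 9% | about 73% |
| 1.5 | 1.0 | 30% | 2.6 / 2.6 | about 3% | about 73% |
| 1.5 | 1.0 | 50% | 2.6 / 2.4 | about 1% | about 73% |
| 0.5 | 0.5 | 0% | 1.1 / 1.4 | about 17% | about 73% |
| 0.5 | 0.5 | 50% | 1.1 / 1.15 | about 4% | about 73% |

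The first two rows are dilution alone. The rows with a cut add offset.

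**Check with a different event model.** Let drug-type events be Poisson, 0.5 per person on placebo and 1.0 on bupropion, with 1.0 alcohol-type event on placebo halved on bupropion. Mean totals are 0.5 + 1.0 = 1.5 and 1.0 + 0.5 = 1.5. The total flags harm in 2.4% of trials and drug-type events alone in about 49%. At 30 per arm the figures are 2.5% and about 57%.

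**Where the gap shrinks.** If three independent side effects each rise from 10% to 40%, with 0.5 background and 0.5 alcohol-caused events and no change in drinking, the total flags harm in about 72%, level with one event type. With alcohol-caused events halved it is about 50%. At the higher rates (1.5 and 1.0, halved) it is about 14%.

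**Limits of the by-type interval.** At 10% v 20% it flags harm in only about 15% of trials. At 10/25 against an expected 2.5/25 it runs from about 6 to 50 points. For seizure the expected number is 25 × 0.001 = 0.025, and the chance of any case is 1 − 0.999^25 = 2.5%, so seizure can be listed but not compared.

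**The case against.** The strongest case against has four parts.

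1. **The offset is not documented.** It requires alcohol-caused events to enter the count. Visits ask about side effects, the participant diary has intoxication as an item of its own, and consequences of drinking are a separate outcome. A reader might infer that falling alcohol-related events will hide bupropion's toxicity. The documents do not support that: they neither include nor exclude such events and give no rates. What stands is that offset is possible and that dilution occurs without it.
2. **The comparison favours the by-type interval.** The main scenario has one event type, fixed in advance, with a 30-point excess. This stands: several side effects rising together can bring the total level, and modest excesses escape both methods.
3. **The plan claims no power.** It says "the respective analyses, are exploratory, and therefore, not powered", so scoring by p<0.05 is not its own criterion. That is fair, and the percentages serve only to compare the two measures. The problem survives under estimation, because an interval for the total does not estimate the excess of any one harm.
4. **Other safety information exists.** Retention captures events that make people leave, and routine tabulation by type is not precluded. The Protection of Human Subjects section and its Table 1 are cited but not in the supplied text. However, that table is described as a summary of procedures and assessments, and retention does not say which harm occurred.

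A reader might also infer that the protocol names several bupropion harms. Only seizure is attributed to the drug. Nausea is an example, and the blood-pressure limit is not tied to bupropion, while General Background lists high blood pressure as a result of drinking.

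**Conclusion.** The point holds as a limitation of the adverse-event measure that is worth correcting. In the supplied text, arms are compared on adverse events only through an undifferentiated count, which is a poor measure for detecting or describing an excess of one side effect. Under the assumed 10% v 40%, the total flags it in about 13% to 26% of trials from dilution alone and about 1% to 4% if alcohol-caused events are recorded and halved, against about 73% for the event type.

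These sizes depend wholly on assumed rates and on a single affected event type. They do not support a general claim that the better bupropion works, the more its harm is masked, nor that a by-type analysis would reliably find modest or rare harms. Nor is it right to infer that the plan has no other tolerability analysis, since retention time is one.

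**What to change.** In the adverse-event paragraph of Statistical Analysis, add for each arm:

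- the number and proportion of participants with at least one event, by event type;
- the number and proportion with an event that led to study medication being held, reduced or stopped;
- for each, the bupropion-placebo difference with a 95% confidence interval (Newcombe or exact), stated to be descriptive.

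Show events recorded as alcohol-related apart from the rest, coded while blinded. List any seizure and any serious event individually. Keep the total count and its ordinal regression as a secondary summary.

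The cost is SAP wording, a few tables and some blinded coding of existing event records; no such coding is described in the supplied text. The intervals will be wide at 25 per arm (roughly ±20 to 25 points), and some types will show an excess by chance, which is why they should be read descriptively. No extra visits or participants are needed, and no change to dosing or clinical rules is proposed.
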